3 INVESTIGATIONAL PLAN

3.1 Study Design and Plan

This is a prospective, multi-center, open-label, single-arm, efficacy, PK, safety and tolerability study of IGSC 20% in subjects with PI. Approximately 60 subjects will be enrolled in order to have approximately 20 adult subjects and 20 pediatric subjects treated with subcutaneously administered IGSC 20% who complete the entire study. This study will include 3 study stages: Screening/Previous Regimen Phase, IGSC 20% Treatment Stage 1 (13 IGSC 20% weekly doses), and IGSC 20% Treatment Stage 2 (39 IGSC 20% weekly doses).

Subjects who are receiving IVIG at a dose of at least 200 mg/kg per infusion every 3 or 4 weeks at Screening must be on a stable IgG regimen (dose and dosing interval) for at least 3 consecutive months prior to Screening. Subjects who are receiving SCIG must also be on a stable regimen for at least 3 consecutive months prior to Screening; there is no prerequisite minimum dose for subjects entering study on an SCIG regimen. Subjects who have never received IVIG or SCIG treatment (treatment naïve) will not be eligible for entry into the study.

Previous Regimen Phase:

- Subjects will be infused with their current ongoing (“previous regimen”) IVIG/SCIG regimen (pIV/pSC) in the clinic (mandatory) to obtain 2 trough IgG levels (obtained prior to each pIV/pSC infusion) on each subject’s “previous regimen”. For subjects entering study on SCIG, the second IgG trough level may be obtained at Baseline, immediately prior to starting the initial infusion of IGSC 20%.
- The Screening Visit may coincide with the pIV/pSC infusion on the previous regimen (pIV#1/pSC#1). Product for the previous IgG regimen is not provided by Grifols. pIV subjects will be enrolled in IGSC 20% Treatment Stage 1 one week after completion of the last IgG trough sampling in the Previous Regimen Phase and therefore the subject must have 2 minimum concentration (C_{trough}) samples on their pIV **prior** to the Baseline/Week 1 visit. pSC subjects will be enrolled in IGSC 20% Treatment Stage 1 (Baseline) in accordance with the time interval that they are currently receiving SCIG (i.e., if on a weekly SCIG regimen, Baseline will occur 1 week after completion of the

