last SCIG infusion and a second IgG trough level will be obtained at Baseline. If the interval between pSC infusions is 2 weeks (or more), then Baseline will occur after that time interval has elapsed, a trough IgG level will be obtained, and the eligible subject may commence IGSC 20% after Baseline assessments are complete).

- Nonconsecutive C_{trough} samples are acceptable for subjects on SCIG. A minimum of 10 days is anticipated for the Screening/Previous Regimen Phase to ensure Screening human immunodeficiency virus (HIV) nucleic acid amplification technology (NAT) test results will be available before the Baseline Visit/Week 1 visit.

20% IGSC Treatment Stage 1:

- The first dose of the IP, IGSC 20%, will be administered immediately after Baseline assessments are complete (SC#1). Subjects will be infused with IGSC 20% at a 1:1 dose-equivalent regimen (per equation in [Section 3.3.2](#)) from their previous regimen at the clinical site (or a minimum IGSC 20% dose of 100 mg/kg/week if the derived 1:1 dose from the previous regimen is lower).
- All subjects will receive 13 IGSC 20% infusions at weekly intervals and study visits at the clinical site will occur at Baseline/SC#1, SC#2, #3, #5, #9, and #13. IgG trough blood levels will be measured at all of these visits (except SC#3) occurring at the clinical site. All other doses of IGSC 20% may be infused at home (once properly trained) or in the clinic.
- The mg/kg dose of IGSC 20% (ratio of mg per kg) will be adjusted at clinic visits if the trough level in subjects is below 500 mg/dL, a level that is considered as insufficient to protect against SBI (40-43); the goal is to avoid repeated dose adjustments. The precise dose adjustment (mg/kg) should not be more than a 15% to 20% increase from the dose producing low IgG trough, per the Investigator's discretion. Any dose adjustments beyond this range will be completed in consultation with the Grifols Medical Monitor. The Treatment Stage 1 dose will continue into IGSC 20% Treatment Stage 2. After the 13th IGSC 20% infusion in IGSC 20% Treatment Stage 1, subjects will enter IGSC 20% Treatment Stage 2 to receive an additional 39 weeks of IGSC 20% therapy.

IGSC 20% Treatment Stage 2:

[figure not shown]

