3.3.2 Selection of Dose and Interval for Each Subject

Screening/Previous Regimen Phase

Subjects will continue their existing (“previous regimen”) IVIG or SCIG regimens (pIV or pSC) during the Screening/Previous Regimen Phase. Product for the Screening/Previous Regimen Phase is not provided by Grifols. Each subject’s established IVIG or SCIG replacement regimen will not be changed throughout the Previous Regimen Phase. Subjects receiving IVIG prior to Screening must receive a dosage of at least 200 mg/kg per infusion, and all subjects must fulfill IgG trough level eligibility criteria ≥ 500 mg/dL (for subjects receiving SCIG prior to Screening, no minimum dosage is required).

The Previous Regimen Phase will include measurement of 2 IgG C_{trough} levels on the subject’s existing IVIG/SCIG treatment regimen. For subjects receiving IVIG, the 2 IgG C_{trough} levels will be obtained prior to each of the 2 IVIG infusions in this Phase (of up to 8 weeks). For subjects receiving SCIG, the 2 IgG C_{trough} levels obtained prior to each of the 2 SC infusions (one week apart or longer interval based on existing previous regimen) will result in a shorter Screening/Previous Regimen Phase time interval of 4 weeks.

All measured C_{trough} levels of IgG drawn pre-Baseline must be ≥ 500 mg/dL for the subject to qualify for Baseline and receipt of study drug (IGSC 20%). If the C_{trough} levels of IgG are < 500 mg/dL on the subject’s existing IVIG or SCIG regimen, the subject will be a Screen Failure. However, the subject may be re-screened once after adjustment in their IgG replacement regimen and maintaining stable dosing for 3 months.

IGSC 20% Treatment Stage 1 and Stage 2

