Dosing: The IGSC 20% mg/kg/week dose to be utilized during Treatment Stage 1 will be calculated based on the subject’s prior (pre-study) pIV or pSC replacement regimen with a 1 to 1 (1:1) correspondence in dosage and a *minimum dose* of IGSC 20% of 100 mg/kg/week. Treatment Stage 1 will commence 7 days after the last IVIG dose or 7 days after the last SC dose of the subject’s previous IgG replacement regimen if on a weekly schedule. If SCIG is given on a biweekly schedule, the dosing interval would be 2 weeks (i.e., the timing of start of Treatment Stage 1 will match the SC dosing interval so that the second SCIG C_{trough} can be obtained immediately prior to dosing with IGSC 20%). During Treatment Stage 1, adjustment in the dose (mg/kg) of IGSC 20% (ratio of mg per kg) will be made at clinic visits

if IgG C_{trough} is less than 500 mg/dL so that adequate immunoglobulin levels are attained. The precise IGSC 20% dose adjustment (mg/kg) should not be more than a 15% to 20% increase (relative to the dose producing low IgG trough), per the Investigator's discretion. Any dose adjustments beyond this range will be completed in consultation with the Grifols Medical Monitor.

The IV regimen to IGSC 20% dose conversion calculation formula is:

$$\frac{\geq 200 \text{ mg/kg (pIV dose)}}{3 \text{ or } 4 \text{ (previous pIV dosing interval in weeks between infusions)}}$$

The alternative SC regimen to IGSC 20% dose conversion calculation formula is:

$$\frac{\text{pSC dose mg/kg}}{\text{previous pSC dosing interval in weeks between infusions}}$$

For subjects on another SCIG regimen at study entry, if the dose is given weekly, the dose of IGSC 20% will be the same. However, if the pre-study SC regimen is dosed over a longer time interval, that dose will be divided by the number of weeks between doses to provide the IGSC 20% dose per week. The minimum dose for IGSC 20% for either case of transition is 100 mg/kg/week.

Weight will be measured at every in-clinic visit and dosing will be based on the subject's most current weight. For the subsequent at home IGSC 20% infusions between clinic visits, the dose will be the same as the total infusion dose calculated at the previous clinic study visit where weight was measured at the clinical site.

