3.6.2.1 Screening Visit and Previous Regimen Phase

Subjects who initially fail to meet eligibility criteria may be re-screened once upon consultation with the Sponsor. Subjects who fail to meet eligibility criteria upon re-screen are screen failures and will not be eligible to participate in the study.

The Previous Regimen Phase for subjects may be between 4 weeks (for subjects entering study on SCIG) and up to 8 weeks (for subjects entering study on IVIG). At the Screening Visit, if a prospective subject is also being dosed (mandatory in-clinic dosing) with their pIV/pSC infusion, in such instances the Screening Visit also becomes a pIV#1 or pSC#1 Visit which shortens the overall duration of this phase. The duration of this phase is also dependent on the need for the HIV screening results that are required prior to Baseline/Week 1 of Treatment Stage 1, which may take up to 2 weeks to report. Another factor which may impact the duration of this phase is the previous IgG dosing frequency (i.e., weekly, biweekly, once every 3 or 4 weeks) in order to ensure 2 previous regimen C_{trough} blood samples are obtained prior to initiation of IGSC 20% dosing in Treatment Stage 1.

ASSESSMENTS AND PROCEDURES DURING SCREENING VISIT AND PREVIOUS REGIMEN PHASE**Screening Visit Assessments for all subjects**

- Informed consent
- Assess inclusion and exclusion criteria ([Section 3.2](#)) to determine subject eligibility
- Assign subject number
- Medical history (record relevant medical history defined as any history impactful on the subject's condition in terms of current functioning, disability, treatment, or management)
- Demography
- Record specific diagnosis of type of PI, date of diagnosis, and date and dose of current IgG replacement regimen initiated
- AEs (including infusion reactions [see [Section 4.3.1](#) for definitions]), prior and concomitant medications assessments (for antibiotics distinguish between prophylactic use and use for treatment of an episode of infection)
- Full physical exam (excludes breast and genitourinary exam)
- Record any SBIs (defined in [Appendix 3](#)) and hospitalizations due to infections (*if this occurs during the Screening/Previous Regimen Phase, the subject will be a Screen Failure*)
- Record non-serious infections (by category) and antibiotic treatment.

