3.6.2.2 Baseline/IGSC 20% SC#1/Week1 (Start of IGSC 20% Treatment Stage 1)

All Screening laboratory results and assessments must be available and all inclusion and exclusion criteria must have been satisfied prior to initiating treatment. Eligible subjects will enter IGSC 20% Treatment Stage 1. There should be no interruption in IgG dosing. The IGSC 20% Treatment Stage 1 should commence 7 days (1 week) after the last previous regimen dose of IVIG or SCIG, except if SCIG is given on a biweekly schedule, the interval would be 2 weeks (i.e., the timing of start of Treatment Stage 1 will match the SC dosing interval so that an accurately reflective, previous regimen IgG C_{trough} can be obtained at Baseline).

The first 3 SC infusions of IGSC 20% will be performed under medical supervision in the Investigator’s clinic (SC#1, SC#2, and SC#3); weekly SC infusions may be administered at home thereafter, once the subject (or parent/guardian if the subject is a child) has been properly trained, and demonstrated to the treating physician his/her competence in administering infusion, use of the SC pump and collection of data on the SC diary.

BASELINE VISIT (WEEK 1)

Assessments to be performed prior to IGSC 20% infusion

- Re-assess inclusion and exclusion criteria ([Section 3.2](#)) to determine subject eligibility (e.g., assure HIV NAT result is negative)
- AEs (including infusion reactions [see [Section 4.3.1](#) for definitions] and clinical observation of signs and symptoms suggestive of any significant disease or condition [e.g., thrombosis, anemia, etc.]
- Prior and concomitant medications assessments (for antibiotics distinguish between prophylactic use and use for treatment of an episode of infection)
- SC infusion diaries: SC/IgG infusion diaries will be provided to each subject at the Baseline visit which may be used to record items including but not limited to: local infusion site reactions, concomitant medications (including antibiotics [prophylactic and therapeutic]), and details of IgG drug administration (location and number of sites,

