10.1.2 Analysis of mean trough total IgG data

Mean trough total IgG concentration for the IGSC 20% treatment phase will be calculated as the average of all steady state trough concentrations measured during the IGSC 20% Treatment Stage 2, ie, total IgG trough levels measured at the following visits: SC#17, #18, #20, #24, #28, #32, #36, #40, #44, #48, #52, and #53. Comparison will be made to the mean trough total IgG concentration for the previous IgG regimen (either IVIG or other SCIG products) obtained during the Screening/Previous Regimen Phase. For subjects entering study on a previous IVIG regimen, the mean trough for the previous IgG regimen will be calculated as the average of the 2 trough concentrations at pIV#1 and pIV#2. For subjects entering study on a previous SCIG regimen, the mean trough for the previous IgG regimen will be calculated as the average of the 2 trough concentrations at pSC#1 and Baseline/SC#1.

Mean trough data will be summarized by study phase. Mean trough summary and analysis will be based on the IgG population. The summaries will be provided by adult vs. pediatric subjects and overall.

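### For SCIG entrants dosed less often than every 2 weeks, the protocol contradicts itself on when Stage 1 starts, so the Baseline sample that the SAP averages as a trough may not be one

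*Protocol*

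**What the plan says.** **Protocol Section 3.6.2.2** starts Stage 1 with a default and one named exception. Stage 1, it says, "should commence 7 days (1 week) after the last previous regimen dose of IVIG or SCIG, except if SCIG is given on a biweekly" regimen, in which case the gap is 2 weeks. The sentence then gives its reason: "the timing of start of Treatment Stage 1 will match the SC dosing interval so that an accurately reflective, previous regimen IgG" trough can be obtained at Baseline.

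**Protocol Section 3.1** has SCIG subjects enter Stage 1 "in accordance with the time interval that they are currently receiving SCIG". It gives 1 week for a weekly regimen and then a general rule: "If the interval between pSC infusions is 2 weeks (or more), then Baseline will occur after that time interval has elapsed". SAP Section 2.1 repeats this.

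**Protocol Section 3.3.2** gives 7 days after the last SC dose of the "previous IgG replacement regimen if on a weekly schedule" and 2 weeks for a biweekly one. It gives no figure for longer intervals but repeats the clause about matching the SC dosing interval.

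**Eligibility.** Inclusion criterion 4 asks for a regimen stable in dose and interval and sets no limit on the SCIG interval. The dose conversion in Section 3.3.2 covers SC regimens given at intervals longer than weekly.

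**Analysis.** For SCIG entrants, SAP Section 10.1.2 says "the mean trough for the previous IgG regimen will be calculated as the average of the 2 trough concentrations at pSC#1 and Baseline/SC#1".

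**The concern.** The previous-regimen mean is the comparator for the first secondary objective, which asks whether trough IgG on IGSC 20% is comparable with trough IgG on the earlier treatment. For an SCIG entrant, the Baseline sample is half of that comparator. If it is drawn 7 days into a 3- or 4-week cycle, it sits well above the trough and the comparator is too high.

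The plan avoids this problem for IVIG entrants. They also start Stage 1 about a week after a long-interval dose, but both of their troughs must be taken before Baseline, and SAP Section 10.1.2 uses pIV#1 and pIV#2. A 3- or 4-weekly SCIG entrant handled under the 7-day default would get the IVIG timing but not the IVIG trough rule.

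No stated check would reliably catch the error. Section 3.6.2.1 requires only that the sample be taken pre-dose, and a day-7 sample before SC#1 meets that. The same section exempts the second SCIG trough from the eligibility check.

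**Working it through.** The plan states no figure to reproduce. The check compares the timing rules and then sizes the consequence under stated assumptions.

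**Step 1: start day by SCIG interval (days after the last SCIG dose)**

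| SCIG interval | Section 3.1 | Section 3.6.2.2, default read literally | Difference | Point in cycle |
|---|---|---|---|---|
| 7 days | 7 | 7 | 0 | 7/7 = 100% |
| 14 days | 14 | 14 | 0 | 14/14 = 100% |
| 21 days | 21 | 7 | 14 days early | 7/21 = 33% |
| 28 days | 28 | 7 | 21 days early | 7/28 = 25% |

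The sections agree for weekly and biweekly regimens and disagree beyond 2 weeks. If the matching clause in Section 3.6.2.2 governs instead, the disagreement disappears. The section therefore supports two answers for the last two rows.

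**Step 2: size for one subject, 28-day cycle, simple decline**

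Assumption: first-order decline with a half-life *h* of 21 to 40 days. The documents give no half-life.

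Ratio of the day-7 value to the day-28 trough = 2^(21/*h*). Comparator inflation, with one true trough and one day-7 value = (1 + ratio)/2 − 1.

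- *h* = 21: ratio 2^1 = 2.00; inflation 50%
- *h* = 30: ratio 2^0.7 = 1.62; inflation 31%
- *h* = 40: ratio 2^0.525 = 1.44; inflation 22%

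**Step 3: the same with slow SC absorption**

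Section 1.4.1 describes an SC depot with slow release, so the calculation was repeated with a steady-state one-compartment model. For dosing interval τ, C(t) is proportional to e^(−kt)/(1 − e^(−kτ)) − e^(−at)/(1 − e^(−aτ)), where k = ln 2/elimination half-life and a = ln 2/absorption half-life. Assumptions: elimination half-life 21 to 35 days, absorption half-life 1 to 3 days, no endogenous IgG.

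- τ = 28: ratio C(7)/C(28) from 1.37 to 1.99; inflation 19 to 49%
- τ = 21: ratio C(7)/C(21) from 1.22 to 1.58; inflation 11 to 29%

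The two models agree on roughly 1.4 to 2.0 times the trough, and 20 to 50% inflation, for a 4-weekly regimen.

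**Step 4: dilution in the group mean**

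The number affected is not given. Assume 60 subjects with similar true troughs and 20 to 50% inflation in each affected 4-weekly subject.

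- One affected: 20/60 to 50/60 = 0.3 to 0.8%
- Five affected: 5 × 20/60 to 5 × 50/60 = 1.7 to 4.2%

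**The case against.** The strongest reply is that the protocol's intent is clear. The sentence with the 7-day default also says that the start matches the SC dosing interval. Section 3.3.2 limits the SCIG 7-day rule to weekly schedules and repeats that clause, and Section 3.1 and SAP Section 2.1 say the same in general terms. On this view only one lead phrase is too broad. Much of this stands. A reader might infer that Section 3.6.2.2 plainly orders a non-trough sample at Baseline, and the documents do not support that. The section is at odds with itself, and harm follows only if a site applies the default and passes over the clause. The default still names just one exception, though, so the wording needs repair.

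Three other stronger readings also go too far:

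- **SCIG more often than weekly.** A reader might infer an equal and opposite error. Section 3.1 gives no start time for such regimens, and the list in Section 3.6.2.1, "previous IgG dosing frequency (i.e., weekly, biweekly, once every 3 or 4 weeks", names nothing more frequent than weekly. The conflict there is only implied.
- **The 4-week phase.** Section 3.3.2 says the SCIG schedule "will result in a shorter Screening/Previous Regimen Phase time interval of 4 weeks", which might seem to rule out two troughs 4 weeks apart. But that sentence allows longer intervals, Section 3.6.1 allows up to 8 weeks, and Section 3.6.2.1 ties the length to dosing frequency so that both troughs are obtained.
- **Table 1-1.** Its 3.5 to 22% changes are cohort means for a switch from IVIG to SCIG. They are no yardstick for an error in one subject.

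The SAP also has general safeguards. Section 4.1.1.2 treats invalid IgG values as missing, and Section 6 has deviations evaluated before database lock. These could catch the problem, but the examples given are hemolysis and a trough drawn after infusion. Time since the last dose is not named.

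Finally, the SAP cites protocol Version 3.0, while the protocol reviewed carries the Version 2.0 change summary. Whether Version 3.0 already settles the wording cannot be seen here. SAP Section 10.1.2 has no timing check in either case.

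**Conclusion.** The contradiction is real and confined to SCIG entrants with intervals over 2 weeks. They are eligible, the protocol gives two answers for when their Baseline falls, and one answer makes the SAP average a non-trough as a trough.

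For a 4-weekly entrant sampled at day 7, that subject's previous-regimen mean would be about 20 to 50% too high, which works against IGSC 20%. This rests on half-lives that are assumed and on a site following the literal default. The number exposed is unknown and may be zero: Section 1.4.1 says SCIG is most commonly given weekly or biweekly. The group-level effect is therefore likely to be small. The mean-trough comparison is summarized without a margin or formal test, and the primary SBI analysis does not use trough values. The point is worth correcting because the correction is cheap. It is not a threat to the trial's main conclusion.

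**What to change.** **Protocol.** Reconcile Sections 3.1, 3.3.2 and 3.6.2.2 so that one consistent statement covers every SCIG interval the entry criteria admit. Which start time is clinically right is for the sponsor to decide; this review takes no view.

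**SAP Section 10.1.2.** Count the Baseline/SC#1 sample as the second previous-SCIG trough only if the recorded time since the last SCIG dose matches the subject's own interval within a stated tolerance. Otherwise use pSC#1 alone and flag the subject. The tolerance has to be written in, because none exists for this visit: Section 3.6.2 gives ±1 day for visits after Baseline and 6 to 9 days after pIV#2 for SC#1.

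**Cost.** Wording in three sections and one derivation rule. A few subjects may have a one-sample comparator. The date of the last SCIG dose must be available, and this should be confirmed. The two SCIG troughs need not be consecutive, so the last dose may not be the in-clinic pSC#1. The infusion diary starts only at Baseline, and the concomitant-medication items listed in Section 3.4 do not explicitly include the date of each dose.

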3.6.2.3 IGSC 20% Treatment Stage 1: Weeks 2 through 13; SC#2 through SC#13

After SC#3 (Week 3), subsequent clinic visits will be at monthly intervals through SC#13 and will include trough (pre-dose) PK IgG levels. **The IGSC 20% mg/kg dose will be adjusted if the trough level is below 500 mg/dL since this level is considered as ineffective against bacterial infection.**

IGSC 20% SC#2 – VISIT IN CLINIC

The second IGSC 20% infusion (SC#2) will be administered at the Investigator's site 1 week post Baseline to provide additional training for the subject. The subject or caregiver should administer the infusion under supervision by site personnel. The following assessments/procedures will be performed:

- Pre-infusion: Draw trough (pre-dose) PK IgG sample
- IGSC 20% dosage will be based on the subject's weight measured in the clinic at Baseline and any adjustment necessary based on the subject's most recent IgG trough level from last visit
- Site personnel will observe (or re-train) subjects/caregivers to self-administer IGSC 20% during this visit using an SC pump
- Document total infusion volume prepared, infusion start date/time and stop date/time, total volume infused, and, if necessary, any infusion interruption with explanation

- Record AEs including infusion reactions (see [Section 4.3.1](#) for definitions) and clinical observation of signs and symptoms suggestive of any significant disease or condition [e.g., thrombosis, anemia, etc.]
- Record concomitant medications (for antibiotics distinguish between prophylactic use and use for treatment of an episode of infection)
- Record any SBIs (defined in [Appendix 3](#)) and hospitalizations due to infections. The evaluations performed to fulfill diagnostic categories specified in [Appendix 3](#) must be recorded in the eCRF.
- Record non-serious infections (by category) and antibiotic treatment.
These include infections of any kind, including, for example, acute sinusitis, exacerbation of chronic sinusitis, acute otitis media, pneumonia, acute bronchitis, infectious diarrhea, etc., which will be recorded as an AE with the Investigator answering the following question affirmatively in the eCRF: “Is this an infection?” (verbatim term delineating nature of infection). Also record validated infections documented by positive radiograph, fever (> 38°C oral or > 39°C rectal), culture, *or* diagnostic testing for microorganisms e.g., bacterial, viral, fungal, or protozoal pathogens (for instance, rapid streptococcal antigen test). The specific evaluations performed to validate infections must be recorded in the eCRF.
- Record days lost from work/school/daily activities due to infections and treatment

IGSC 20% SC#3 – VISIT IN CLINIC

The third IGSC 20% infusion (SC#3) will also be administered at the Investigator’s site to provide additional experience for the subject/caregiver. The subject or caregiver should administer the infusion under supervision by site personnel. The following assessments/procedures will be performed:

- IGSC 20% dosage will be based on the subject’s weight measured in the clinic at Baseline and any adjustment necessary based on the subject’s most recent IgG trough level from last visit
- Site personnel will observe (or re-train) subjects/caregivers to self-administer IGSC 20% during this visit using an SC pump
- Document total infusion volume prepared, infusion start date/time and stop date/time, total volume infused, and, if necessary, any infusion interruption with explanation
- Record AEs including infusion reactions (see [Section 4.3.1](#) for definitions) and clinical observation of signs and symptoms suggestive of any significant disease or condition [e.g., thrombosis, anemia, etc.]
- Record concomitant medications (for antibiotics distinguish between prophylactic use and use for treatment of an episode of infection)
- Record any SBIs (defined in [Appendix 3](#)) and hospitalizations due to infections. The evaluations performed to fulfill diagnostic categories specified in [Appendix 3](#) must be recorded in the eCRF.
- Record non-serious infections (by category) and antibiotic treatment.

These include infections of any kind including for example acute sinusitis, exacerbation of chronic sinusitis, acute otitis media, pneumonia, acute bronchitis, infectious diarrhea, etc., which will be recorded as an AE with the Investigator answering the following question affirmatively in the eCRF: “Is this an infection? (verbatim term delineating nature of infection). Also record validated infections documented by positive radiograph, fever ($> 38^{\circ}\text{C}$ oral or $> 39^{\circ}\text{C}$ rectal), culture, *or* diagnostic testing for microorganisms e.g., bacterial, viral, fungal, or protozoal pathogens (for instance, rapid streptococcal antigen test). The specific evaluations performed to validate infections must be recorded in the eCRF.

- Record days lost from work/school/daily activities due to infections and treatment

IGSC 20% SC#5, 9, AND 13 – VISITS IN CLINIC

Assessments to be performed prior to IGSC 20% infusion at all Visits:

- Full physical exam (excludes breast and genitourinary exam) at SC#13 Visit only
- Weight
- Vital signs (T, RR, HR, SBP, DBP)
- Trough (pre-dose) PK IgG sampling
- Review of trough (pre-dose) PK IgG level to assure C_{trough} is not less than 500 mg/dL. Adjustment in dose of IGSC 20% will be necessary if IgG C_{trough} is below this threshold. The dose adjustment (mg/kg) should not be more than a 15% to 20% increase from the dose producing the low IgG trough, per the Investigator’s discretion. Any dose adjustments beyond this range will require consultation with Grifols. Use weight from current visit to calculate the total dose of IGSC 20% to be administered on-site and subsequently at home at weekly intervals.
- Review SC infusion diary and infusion details from IGSC 20% administered weekly at home with subjects/caregivers. All local infusion site reactions will be recorded in the eCRF. The subset of local infusion site reactions where the symptoms/signs lead to infusion interruption or discontinuation, require concomitant medication, or have an impact on the general condition of the subject as judged by the Investigator will be considered as AEs.
- Record any SBIs (defined in [Appendix 3](#)) and hospitalizations due to infections. The evaluations performed to fulfill diagnostic categories in [Appendix 3](#) must be recorded in the eCRF.
- Record non-serious infections (by category) and antibiotic treatment.

These include infections of any kind including for example acute sinusitis, exacerbation of chronic sinusitis, acute otitis media, pneumonia, acute bronchitis, infectious diarrhea, etc., which will be recorded as an AE with the Investigator answering the following question affirmatively in the eCRF: “Is this an infection? (verbatim term delineating nature of infection). Also record validated infections documented by positive radiograph, fever ($> 38^{\circ}\text{C}$ oral or $> 39^{\circ}\text{C}$ rectal), culture, *or* diagnostic testing for microorganisms e.g., bacterial, viral, fungal, or protozoal pathogens (for instance, rapid streptococcal

antigen test). The specific evaluations performed to validate infections must be recorded in the eCRF.

- Record days lost from work/school/daily activities due to infections and treatment

IP infusion in clinic at Visits SC#5, SC#9, and SC#13

- IGSC 20% dose will be based on the subject's weight measured in the clinic at SC#5, SC#9, and SC#13 Visits and any adjustment necessary based on the subject's most recent IgG trough level from last visit
- An infusion pump (designed for SC infusion) will be used to deliver IGSC 20%
- Site personnel will observe subjects/caregivers administering IGSC 20% and retrain if needed. This will be documented.
- Document total infusion volume prepared, infusion start date/time and stop date/time, total volume infused, and, if necessary, any infusion interruption with explanation
- Record AEs including infusion reactions (see [Section 4.3.1](#) for definitions) and clinical observation of signs and symptoms suggestive of any significant disease or condition [e.g., thrombosis, anemia, etc.]
- Record concomitant medications (for antibiotics distinguish between prophylactic use and use for treatment of an episode of infection)

IP infusion may be administered at home for intervening weekly infusions, specifically infusion numbers SC#4, SC#6, SC#7, SC#8, SC#10, SC#11, and SC#12. The SC infusion diary must be completed with all relevant information pertaining to infusion particulars as detailed in [Section 3.6.2.2](#). The weight that will be used to determine the infusion dose will be the most recent weight obtained at the last clinic visit.

Laboratory draw and height at SC#13 visit only prior to IGSC 20% infusion:

- Height
- Sample for IgG subclass levels, and antibody titers for bacterial pathogens (*H. influenzae*, *S. pneumoniae*, *C. tetani* [tetanus])
- Blood and urine samples for clinical laboratory assessments (clinical chemistry, hematology, urinalysis, additional special tests) (see [Section 3.6.3](#)):
 - Hemoglobin, hematocrit, platelets, red blood cell count including red blood cell morphology, white blood cell count with differential, ARC
 - Additional Special Tests: Direct antiglobulin test (DAT), serum free hemoglobin, haptoglobin
 - Sodium, potassium, creatinine, chloride, calcium, BUN, bicarbonate, albumin, LDH, AST, ALT, ALP, glucose, total bilirubin, indirect bilirubin
 - Urinalysis: pH, protein, glucose, ketones, bilirubin, nitrites, urobilinogen, blood, leukocyte esterase (with microscopic examination of urine sediment if abnormal)

